## PROTOCOL SYNOPSIS

TITLE	Intradetrusor Onabotulinumtoxin A (Botox®) at the time of Transurethral Resection of the Prostate or Transurethral Waterjet Ablation of the Prostate for Mixed Lower Urinary Tract Symptoms
NUMBER OF SITES	1
RATIONALE	
Patients with longstanding obstructive lower urinary tract symptoms (LUTS) due to benign prostatic hypertrophy (BPH) can also develop symptoms of overactive bladder syndrome (OAB). Transurethral resection of the prostate (TURP) and Transurethral Waterjet Ablation of the Prostate (Aquablution®) are amongst the gold standard surgical treatments for BPH. However, in the immediate post-operative period, TURP and Aquablution® can also include OAB-like symptoms, including urinary frequency and urgency. For men with baseline OAB symptoms, this initial worsening of symptoms can be distressing.
 
Botox® is an FDA approved medication with on-label indications to treat overactive bladder.
 
The purpose of this study is to evaluate the outcomes of men who have Botox® concurrent with their TURP or Aquablution®.

STUDY DESIGN	This is an observational study to close knowledge gaps on the outcomes of patients who undergo these procedures concurrently.
PRIMARY OBJECTIVE	To identify whether concurrent Botox® and TURP or Aquablution® are effective at reducing post-operative irritative voiding symptoms.
SECONDARY OBJECTIVES	To identify whether concurrent Botox® and TURP or Aquablution® lead to higher rates of urinary retention, longer hospitalization.
NUMBER OF SUBJECTS	The goal will be to enroll 20 subjects
SELECT SUBJECT ENTRANCE CRITERIA	
Inclusion Criteria:
 
 
1. Male <math>\geq</math> 18 years of age and being scheduled to undergo TURP or Aquablution® and Botox® procedure.
 
2. Written informed consent obtained from subject and ability for subject to comply with the requirements of the study.
 
 
Exclusion Criteria:
 
 
3. Non-English speaking
 
4. Presence of a condition or abnormality that in the opinion of the Investigator would compromise the safety of the patient or the quality of the data.
 

	5. History of receiving Botox® in the bladder, within the previous 12 months.
DURATION OF SUBJECT PARTICIPATION AND DURATION OF STUDY	Total expected duration of participation is four months. The study is expected to last approximately 2 years.
CONCOMITANT MEDICATIONS	All concomitant medications are allowed.
PRIMARY ENDPOINT	
 
1 week post-operative visit for: trial of void, to assess for rates of postoperative urinary retention.
 

SECONDARY ENDPOINTS	
 
4 and 12 week post-operative visits for: post void residual assessment via bladder scan, AUA symptom score, PGI-I, UDI-6, and VM Post Procedure questionnaires will be administered
 
Hospitalization readmission rates, urinary retention episodes
 

SAFETY EVALUATIONS	All subjects will be closely monitored per standard of care by their urology provider.
PLANNED INTERIM ANALYSES	None
STATISTICS Primary Analysis Plan	Descriptive statistics will be performed for demographic and survey data.

## 1. STUDY OBJECTIVES

### 1.1 Primary Objectives

To identify whether concurrent Botox® and TURP or Aquablation® are effective at reducing post-operative irritative voiding symptoms.

### 1.2 Secondary Objectives

To identify whether concurrent Botox® and TURP or Aquablation® lead to higher rates of urinary retention, longer hospitalization.

### 1.3 Primary Endpoint

1 week post-operative visit for: trial of void, to assess for rates of postoperative urinary retention.

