### 1.4 Secondary Endpoints

Four and twelve-week post-op visits when AUA symptom score, VM Post Procedure Questionnaire, PGI-I, and UDI-6 questionnaires will be administered. Post void residual obtained via bladder scan.

Hospitalization readmission rates, urinary retention episodes.

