## 2. BACKGROUND

### 2.1 Rationale

Patients with longstanding obstructive lower urinary tract symptoms (LUTS) due to benign prostatic hypertrophy (BPH) can also develop symptoms of overactive bladder syndrome (OAB). Transurethral resection of the prostate (TURP) and Transurethral Waterjet Ablation of the Prostate (Aquablation®) are amongst the gold standard surgical treatments for BPH. However, in the immediate post-operative period, TURP and Aquablation® can also include OAB-like symptoms, including urinary frequency and urgency. For men with baseline OAB symptoms, this initial worsening of symptoms can be distressing.

Botox® is an FDA approved medication with on-label indications to treat overactive bladder.

The purpose of this study is to evaluate the outcomes of men who have Botox® concurrent with their TURP or Aquablation®.

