### 2.2 Supporting Data

Benign prostatic hypertrophy (BPH) is the natural growth of the prostate in aging men. BPH can eventually lead to an obstructed urinary stream, urinary

retention, and renal damage (1). It can additionally lead to both a hypocontractile as well as a hypercontractile, or overactive bladder (OAB). OAB is defined by irritative voiding symptoms, such as urinary frequency, urinary urgency, urge incontinence, and nocturia (2).

Transurethral resection of the prostate and Aquablation® are endoscopic procedures. In the case of TURP, a camera and resecting tool (resectoscope) are introduced via the urethra and the overgrown prostate is removed. This procedure is performed in the operating room under general or spinal anesthesia. Aquablation® is performed by placing a camera in the urethra and vaporizing prostatic tissue with a pressurized beam of water. Transurethral resection of the prostate and Aquablation® are considered amongst the gold standard treatment for BPH and obstructive LUTS (3,4,5).

However, for men with BPH and OAB, surgical treatment of BPH alone may not alleviate symptoms of overactivity (6). Furthermore, in the immediate post-operative period, TURP and Aquablation® can exacerbate symptoms of overactivity (7), causing distress to patients.

Overactive bladder has its own treatment pathway as outlined in the combined AUA/SUFU guideline (8,9). Botox® is administered as a 100 U starting dose via an endoscopic approach and can be up-titrated. The effect lasts, on average, 6-9 months at which point the injection can be repeated. Typically, Botox® injection is well tolerated and can be performed in the clinic with local anesthesia, although some patients prefer Botox® injection in the operating room (10). Recently, there has been rising concern regarding the safety profile of second line OAB treatments and a push to move to third line treatments for long-term management (11).

Currently, there is no data on the treatment outcomes or patient satisfaction of performing Botox® at the time of TURP or Aquablation®.

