### 3. STUDY DESIGN

#### 3.1 Observational Study

An observational study of the effect of Botox® injection at the time of TURP or Aquablation® will be performed.

If deemed eligible, participants will be invited to participate in this trial. The decision to accept or decline participation in the study will have no impact on whether they receive either treatment. After informed consent is obtained, patients will be administered the AUA symptom score and the Urinary Distress Inventory Short Form (UDI-6) as measures of baseline symptom severity and bother.

The International Prostate Symptom Score (IPSS) is a questionnaire that is widely used to assess LUTS in patients and assesses for incomplete emptying, frequency, intermittency, urgency, weak stream, hesitancy, and nocturia. The AUA quality of life score (AUA-QoL) asks how these symptoms affect quality of life. When administered as a combined questionnaire, this is referred to as the AUA symptom score. These scores are summed to produce an overall severity score, which can categorize patients as having mild (score 0-7), moderate (8-19) or severe (20-35) LUTS (12). The AUA symptom score is a benchmark in defining the severity of symptoms, and collection of these scores is recommended in the AUA guidelines as part of the initial management of BPH (3,4,13). The UDI-6 is a validated short form of the urogenital distress inventory, and it assesses for the impact and severity of urinary incontinence (14).

Participants will then undergo their TURP or Aquablation® and Botox® procedure with one of three surgeons in the department of Urology at Virginia Mason.

At approximately four weeks post-op, participants will have a visit with their provider. Symptoms will be assessed by re-administering the AUA symptom score, the UDI-6, PGI-I and the VM Post-Procedure Questionnaire to assess for change in symptoms as well as satisfaction with their procedure.

Participants will then have an approximate 3 month post-op visit, at which time the questionnaires will be re-administered. Patients will have the opportunity to follow-up with their provider sooner, if needed, based on individual symptoms.

The total expected duration of participation for any given participant is 4 months.

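### The primary endpoint, a 1-week trial of void for urinary retention, does not measure the primary objective, which is a reduction in irritative voiding symptoms

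*Protocol*

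**What the plan says.** The primary objective in Section 1.1, repeated in the synopsis, reads: "To identify whether concurrent Botox® and TURP or Aquablation® are effective at reducing post-operative irritative voiding symptoms". The secondary objective in Section 1.2 asks whether the combined procedures "lead to higher rates of urinary retention, longer hospitalization".

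The only primary endpoint, in Section 1.3 and again in the synopsis, is "1 week post-operative visit for: trial of void, to assess for rates of postoperative urinary retention". The symptom measures come one level down, in Section 1.4: "Four and twelve-week post-op visits when AUA symptom score, VM Post Procedure Questionnaire, PGI-I, and UDI-6 questionnaires will be administered". That section also lists post-void residual, readmission and episodes of retention.

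Section 3.1 says the AUA symptom score and UDI-6 are given after consent, describing the AUA score and the Urinary Distress Inventory "Short Form (UDI-6) as measures of baseline symptom severity and bother". PGI-I and the VM questionnaire are given only after surgery.

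**The concern.** A primary endpoint should be the measurement that answers the primary question. Here the question concerns symptoms and the measurement concerns bladder emptying. A trial of void shows whether a man can empty his bladder one week after surgery. It does not record frequency, urgency, urge incontinence or nocturia.

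The danger lies in reporting. A favourable retention proportion could be presented as success on the primary endpoint of a study whose declared aim is symptom relief, when that figure carries no information on symptoms. Hypothesis d in Section 5.1 makes a later randomized study depend on these results, so the confusion could carry forward.

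**Working it through.** The protocol states no figure for this point, so the check is a comparison of its sections.

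| Level | Objective | Hypothesis (5.1) | Endpoint listed at that level |
|---|---|---|---|
| Primary | Fewer irritative symptoms (1.1) | b: improvement from baseline | 1-week trial of void for retention (1.3) |
| Secondary | Retention, hospitalization (1.2) | c: no increase in morbidity, retention or readmission | AUA score, UDI-6, PGI-I, VM questionnaire, post-void residual, readmission, retention episodes (1.4) |

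**Is retention an irritative symptom in this protocol?** No. Section 2.2 names frequency, urgency, urge incontinence and nocturia as examples. It mentions retention separately, as a consequence of obstruction.

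**Is it a slip in one place?** No. The synopsis and the body carry the same objective and the same endpoint, and no section reconciles them. Hypotheses b and c keep the two questions apart.

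**What does the rest of the text point to?** Section 2.1 motivates the study by symptoms: "in the immediate post-operative period, TURP and Aquablation® can also include OAB-like symptoms, including urinary frequency and urgency". The one external comparison, at the end of Section 3.1, is with published rates of overactivity and bother after surgery alone. The narrative in Section 3.1 goes from the operation to a visit at about four weeks and does not describe the 1-week visit that carries the primary endpoint. Retention itself appears in three forms: primary in 1.3, episodes in 1.4, and a 30-day rate in 3.1.

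**Where are the symptom data?** Section 3.1 uses four questionnaires at follow-up to assess symptom change and satisfaction. All 4 are secondary. A baseline exists for 2 of the 4, the AUA score and UDI-6.

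**Would the AUA total be an adequate replacement?** This matters only for the repair. Section 3.1 says the questionnaire "assesses for incomplete emptying, frequency, intermittency, urgency, weak stream, hesitancy, and nocturia": seven symptoms, with a maximum total of 35.

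- Assume equal weights and a quality-of-life item outside the total: 35 / 7 = 5 points per symptom.
- Irritative under Section 2.2: frequency, urgency, nocturia. 3 × 5 = 15 points; 15 / 35 = 43%.
- Emptying and flow: incomplete emptying, intermittency, weak stream, hesitancy. 4 × 5 = 20 points; 20 / 35 = 57%.
- If the quality-of-life item were instead an eighth equal part of the total, the irritative share would be 3 / 8 = 37.5%.

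Under either assumption less than half of the total reflects irritative symptoms. A fall in it after prostate surgery could come mainly from relief of obstruction, so a symptom endpoint has to name the items.

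**The case against.** The strongest reply is that little hangs on the label. This is a single-site observational study of 20 men. Its size is set by clinic volume, its analysis is descriptive, and it has no interim look, alpha, power or decision rule. All the symptom data are collected anyway. This is correct, and it limits the consequence to interpretation and reporting. It does not make the endpoint answer the objective.

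A second reply is that retention may be the intended focus. Section 2.1 gives the purpose broadly as evaluating outcomes, and hypothesis d leaves better evaluation of symptom improvement to a later randomized study. That reading is coherent, but Section 1.1 then states the wrong objective. It bears on which repair to choose, not on whether one is needed.

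Three narrower points stand:

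- A mean change on three AUA items matches hypothesis b, but it is not directly comparable with the published rates mentioned in Section 3.1.
- PGI-I and the VM questionnaire are hardly described, so the case rests mainly on the AUA score and UDI-6.
- The choice of a leading instrument and visit among secondary measures may be made in an analysis plan not shown here, and is not counted as a defect.

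An analysis plan cannot cure the main point, however. The protocol states both the objective and the endpoint, and they conflict.

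**Conclusion.** The concern holds and must be fixed: the protocol is wrong as written. The primary endpoint gives no information on the primary objective, and the mismatch stands in both the synopsis and the body. The conclusion rests on the text alone. The 43% and 57% shares apply only if the AUA total is considered as a replacement, and they depend on the weighting assumptions stated with them.

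Power and type I error are untouched, since the target of 20 is derived from neither endpoint. A lesser gap of the same kind is that Section 1.2 asks about longer hospitalization and Section 3.1 collects length of stay, but Section 1.4 does not list it.

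**What to change.** Choose one of two repairs and apply it in the synopsis and the body.

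1. **Keep the symptom objective.** In Section 1.3, make the primary endpoint the within-patient change from baseline in the AUA frequency, urgency and nocturia items at one named visit. Of the visits with questionnaires, week 4 is the closest to the early post-operative period that motivates the study; the protocol itself ranks neither week 4 nor week 12 first. Use change in UDI-6 as support, because the listed AUA symptoms do not include urge incontinence. Move the 1-week trial of void to Section 1.4 as the main safety endpoint for objective 1.2. State that, without a concurrent control, the endpoint describes change after the combined procedure and does not isolate the effect of Botox. If the comparison with published rates is kept, report a proportion defined as in the published source alongside the mean change.
2. **Keep the retention endpoint.** Restate Section 1.1 as estimating the 1-week retention rate after the combined procedure, and make symptom change a secondary objective in Section 1.2.

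Under either repair, list length of stay in Section 1.4 and describe the 1-week visit in Section 3.1.

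The cost is a wording amendment with IRB approval before implementation, as Section 7.1 requires. No new patients, visits or instruments are needed. The change should be made before outcomes are examined; if they already have been, report it openly as a late change, with its date and reason.

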### 1.4 Secondary Endpoints

Four and twelve-week post-op visits when AUA symptom score, VM Post Procedure Questionnaire, PGI-I, and UDI-6 questionnaires will be administered. Post void residual obtained via bladder scan.

Hospitalization readmission rates, urinary retention episodes.

## 2. BACKGROUND

### 2.1 Rationale

Patients with longstanding obstructive lower urinary tract symptoms (LUTS) due to benign prostatic hypertrophy (BPH) can also develop symptoms of overactive bladder syndrome (OAB). Transurethral resection of the prostate (TURP) and Transurethral Waterjet Ablation of the Prostate (Aquablation®) are amongst the gold standard surgical treatments for BPH. However, in the immediate post-operative period, TURP and Aquablation® can also include OAB-like symptoms, including urinary frequency and urgency. For men with baseline OAB symptoms, this initial worsening of symptoms can be distressing.

Botox® is an FDA approved medication with on-label indications to treat overactive bladder.

The purpose of this study is to evaluate the outcomes of men who have Botox® concurrent with their TURP or Aquablation®.

### 2.2 Supporting Data

Benign prostatic hypertrophy (BPH) is the natural growth of the prostate in aging men. BPH can eventually lead to an obstructed urinary stream, urinary

retention, and renal damage (1). It can additionally lead to both a hypocontractile as well as a hypercontractile, or overactive bladder (OAB). OAB is defined by irritative voiding symptoms, such as urinary frequency, urinary urgency, urge incontinence, and nocturia (2).

Transurethral resection of the prostate and Aquablation® are endoscopic procedures. In the case of TURP, a camera and resecting tool (resectoscope) are introduced via the urethra and the overgrown prostate is removed. This procedure is performed in the operating room under general or spinal anesthesia. Aquablation® is performed by placing a camera in the urethra and vaporizing prostatic tissue with a pressurized beam of water. Transurethral resection of the prostate and Aquablation® are considered amongst the gold standard treatment for BPH and obstructive LUTS (3,4,5).

However, for men with BPH and OAB, surgical treatment of BPH alone may not alleviate symptoms of overactivity (6). Furthermore, in the immediate post-operative period, TURP and Aquablation® can exacerbate symptoms of overactivity (7), causing distress to patients.

Overactive bladder has its own treatment pathway as outlined in the combined AUA/SUFU guideline (8,9). Botox® is administered as a 100 U starting dose via an endoscopic approach and can be up-titrated. The effect lasts, on average, 6-9 months at which point the injection can be repeated. Typically, Botox® injection is well tolerated and can be performed in the clinic with local anesthesia, although some patients prefer Botox® injection in the operating room (10). Recently, there has been rising concern regarding the safety profile of second line OAB treatments and a push to move to third line treatments for long-term management (11).

Currently, there is no data on the treatment outcomes or patient satisfaction of performing Botox® at the time of TURP or Aquablation®.

### 3. STUDY DESIGN

#### 3.1 Observational Study

An observational study of the effect of Botox® injection at the time of TURP or Aquablation® will be performed.

If deemed eligible, participants will be invited to participate in this trial. The decision to accept or decline participation in the study will have no impact on whether they receive either treatment. After informed consent is obtained, patients will be administered the AUA symptom score and the Urinary Distress Inventory Short Form (UDI-6) as measures of baseline symptom severity and bother.

The International Prostate Symptom Score (IPSS) is a questionnaire that is widely used to assess LUTS in patients and assesses for incomplete emptying, frequency, intermittency, urgency, weak stream, hesitancy, and nocturia. The AUA quality of life score (AUA-QoL) asks how these symptoms affect quality of life. When administered as a combined questionnaire, this is referred to as the AUA symptom score. These scores are summed to produce an overall severity score, which can categorize patients as having mild (score 0-7), moderate (8-19) or severe (20-35) LUTS (12). The AUA symptom score is a benchmark in defining the severity of symptoms, and collection of these scores is recommended in the AUA guidelines as part of the initial management of BPH (3,4,13). The UDI-6 is a validated short form of the urogenital distress inventory, and it assesses for the impact and severity of urinary incontinence (14).

Participants will then undergo their TURP or Aquablation® and Botox® procedure with one of three surgeons in the department of Urology at Virginia Mason.

At approximately four weeks post-op, participants will have a visit with their provider. Symptoms will be assessed by re-administering the AUA symptom score, the UDI-6, PGI-I and the VM Post-Procedure Questionnaire to assess for change in symptoms as well as satisfaction with their procedure.

Participants will then have an approximate 3 month post-op visit, at which time the questionnaires will be re-administered. Patients will have the opportunity to follow-up with their provider sooner, if needed, based on individual symptoms.

The total expected duration of participation for any given participant is 4 months.

Demographic data, including comorbidities, urodynamics results, post-void residual, uroflow, operative length, estimated blood loss, length of stay, 30 day readmission rate, and 30 day rate of urinary retention will be collected for each subject via the electronic medical record.

All data will be entered into a secure password-protected clinical research database maintained on a Virginia Mason computer.

The goal is to enroll 20 patients based on an estimation of eligible subjects seen within the Virginia Mason urology outpatient clinic. The rate of enrollment is expected to be 1-2 patients per month.

We will be evaluating the impact of Botox® concurrent with TURP or Aquablation® relative to published rates of overactivity and bother after TURP or Aquablation® alone.

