##### 4.3 *Data Collection Procedures*

Virginia Mason Urology providers will identify patients for potential study participation.

Informed consent will be obtained for all subjects who wish to participate in this trial. Upon consent, study staff will obtain baseline and demographic data, administer AUA symptom score and the UDI-6. At follow up visits, the AUA symptom score, UDI-6, PGI-I, and VM post-procedure questionnaire will be obtained for participating patients. Additional data points under study will be obtained from the subject's electronic medical record.

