#### 5. STATISTICAL CONSIDERATIONS

##### 5.1 *Hypotheses*

- a. There is a high rate of bother from OAB symptoms in men with BPH
- b. Botox® injection at the time of TURP or Aquablation® will improve irritative symptoms as compared to baseline.
- c. Botox® injection at the time of TURP or Aquablation® will not increase procedural morbidity, urinary retention rate, or readmission rate.
- d. Plan for future randomized, single-blind study to better evaluate symptomatic improvement pending the results of the study.

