## 6. DATA COLLECTION

### 6.1 Records to be kept

Clinical and demographic data is available through electronic medical records and will be entered directly into the study database. Any paper study documents that are generated, such as the questionnaires, will be securely stored and archived for 10 years following study completion.

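### No step is described for finding readmissions, or retention episodes between visits, that are treated elsewhere, so these two secondary-endpoint rates may be understated

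*Protocol*

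**What the plan says.** Protocol section 1.4 lists among the secondary endpoints "Hospitalization readmission rates, urinary retention episodes". It gives no data source or time window there. Section 3.1 supplies both: "30 day readmission rate, and 30 day rate of urinary retention will be collected for each subject via the electronic medical record".

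Two other sections point to the same source. Section 4.3, after listing the questionnaires, says "Additional data points under study will be obtained from the subject's electronic medical record". Section 6.1 says "Clinical and demographic data is available through electronic medical records and will be entered directly into the study database".

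Retention is also assessed in person. The primary endpoint in section 1.3 is a 1-week visit for "trial of void, to assess for rates of postoperative urinary retention". For the 4- and 12-week visits, section 1.4 adds "Post void residual obtained via bladder scan". Section 3.1 gives the purpose of the follow-up questionnaires as "to assess for change in symptoms as well as satisfaction with their procedure".

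Hypothesis c in section 5.1 is that adding the injection "will not increase procedural morbidity, urinary retention rate, or readmission rate".

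**The concern.** Acute retention and early readmission are often unplanned, and a man may go to whichever emergency department is nearest. If that is not the study hospital, the event reaches the study database only if the outside record is shared or someone asks and charts the answer. The protocol describes neither.

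A missed event is counted as no event, so the error can go only one way: the observed rate is too low. Section 1.2 makes higher retention a secondary objective, and section 2.2 says that no outcome data exist for the combined procedure. Section 5.1 makes a future randomized study depend on these results. A harm rate that is too low would carry into that decision. How events are found has to be settled before the visits take place, because a question not asked at 4 or 12 weeks is hard to replace later.

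**Working it through.** **Step 1. Which events have a second route?** The named sources, set side by side:

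| Event | Electronic record (3.1, 4.3, 6.1) | In-person check (1.3, 1.4) | Described step to find care elsewhere |
|---|---|---|---|
| Retention present at a visit | yes | trial of void at 1 week; bladder scan at 4 and 12 weeks | not needed |
| Retention episode treated and resolved between visits | yes | none | none |
| Readmission | yes | none | none |

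For example, a man catheterised elsewhere in week 2 who empties normally by week 4 passes the 1-week trial of void and the 4-week scan. Only the record could show his episode. The gap is therefore between-visit retention episodes and readmissions, not retention as a whole.

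**Step 2. Size per missed event.** The enrolment goal is 20 (section 3.1). One missed patient-event lowers a rate by 1/20 = 5 percentage points. If 3 men truly had an event (3/20 = 15%), missing one gives 2/20 = 10%, and missing two gives 1/20 = 5%.

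**Step 3. Range.** The protocol gives neither an event rate nor the share of events that the record captures, so both are assumptions here. With true rate p and capture share s:

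- expected observed rate = p × s
- chance of missing at least one event among 20 men = 1 − (1 − p(1 − s))^20

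| True rate p | Capture s | Expected observed rate | Chance of at least one missed event |
|---|---|---|---|
| 5% | 80% | 4% | 1 − 0.99^20 = 18% |
| 10% | 80% | 8% | 1 − 0.98^20 = 33% |
| 20% | 80% | 16% | 1 − 0.96^20 = 56% |
| 5% | 50% | 2.5% | 1 − 0.975^20 = 40% |
| 10% | 50% | 5% | 1 − 0.95^20 = 64% |
| 20% | 50% | 10% | 1 − 0.90^20 = 88% |
| any | 100% | p | 0% |

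**Step 4. Scale against sampling error.** Exact 95% (Clopper-Pearson) intervals at n = 20 are 0 to 16.8% for 0/20, 0.1 to 24.9% for 1/20 and 1.2 to 31.7% for 2/20. Imprecision is larger than the likely undercount. But the interval is built on the events counted and makes no allowance for those missed.

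**Step 5. Does the visit schedule suit a fix?** The first questionnaire visit is at about 4 weeks (28 days), just short of the 30-day window. A question asked only then would leave the last days uncovered. Asking again at 12 weeks, with dates, completes the window.

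**The case against.** The strongest reply is that the record may already hold these events. The protocol does not say that it is limited to the study hospital or lacks outside encounters; one site does not settle what its record contains. Every man sees his provider at about 4 weeks and can come sooner if symptoms require, and the synopsis provides for close standard-of-care monitoring by the urology provider. A urologist could well hear of a catheter or an admission and chart it. The items of the VM Post-Procedure Questionnaire are not shown, so it might ask. The study is also small and descriptive, and using the record for 30-day outcomes is a stated choice.

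Much of this stands. It makes the undercount conditional and its size unknown, with zero possible. It does not remove the gap: hearing of an event informally depends on the man and the provider, and the stated purpose of the questionnaires is symptom change and satisfaction.

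Two stronger readings are tempting, and the document supports neither:

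- **That retention is collected from the record alone, with visits that contain only questionnaires.** Sections 1.3 and 1.4 provide a trial of void and bladder scans.
- **That the rates are biased in favour of hypothesis c.** A claim of no increase needs a reference rate, and the only comparator that section 3.1 names is published figures for overactivity and bother. None is named for retention or readmission. If a published rate were used that had the same incomplete capture, the comparison need not favour hypothesis c.

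**Conclusion.** The point holds in a limited form. For readmission, the electronic record is the only named source. For retention, the episodes at risk are those treated elsewhere and resolved between visits. The primary endpoint, a test done at the 1-week visit, is not affected.

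If events are missed, the observed secondary-endpoint rates are too low, by 5 percentage points per missed patient-event with 20 men. That direction is certain. Whether any events are missed, and how many, cannot be determined from the protocol: the capture shares of 50% and 80% and the true rates of 5% to 20% used above are assumptions, and at full capture there is no error. The direction of error relative to a comparator is not established. This is a better way of finding events than the one stated, and not the correction of a contradiction.

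**What to change.** In sections 3.1 and 4.3, have study staff ask every man a fixed question at the existing 4- and 12-week visits: any emergency visit, catheter placement or overnight admission at any hospital since he was last asked, with the date. At the 4-week visit the look-back should start at discharge after the operation, so that the first week is covered. The 12-week answer then completes the 30-day window, and the dates show which events fall inside it.

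Count an event if it is in the record or reported by the man, count it once if both, and report how many came from the record, from the man or from both.

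The cost is one short item at visits already planned, with no added visit and no change to treatment. The downside is that some self-reported events will lack outside records, and reporting the source lets readers judge those.
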